4.2.1 Visit schedule and assessments

Table 2 visit schedule and assessments

Trial Period	Screening	Treatment Period			
Visit	1	2	3	4	5
Study Week	0	8	16	20	28
Days from randomization	-56	0	56	84	140
Informed Consent	X				
Inclusion/Exclusion Criteria	X	X			
Medical History	X				
Concomitant therapy	X	X	X	X	X
Demographics	X				
Physical Exam	X	X			
Vital Signs	X	X	X	X	X
Height	X				
Weight	X	X	X	X	X
Randomization		X			
Pregnancy test ¹	X	X		X	X
Home Blood glucose monitoring ²		X	X	X	X
Safety blood samples ³	X	X	X		X
HbA _{1c}	X		X		X
Device Interrogation	X	X	X	X	X
Monitor Counter Reset	X	X	X	X	X
12 Lead Holter ECG for 24hrs		X	X		X
Echocardiography	X ⁴	X	X		X
NT-Pro-BNP		X	X	X	X
Medication Compliance check			X		X

¹ For female patients with childbearing potential (Urine pregnancy test).

[figure not shown]
² Patients without means for daily home blood glucose monitoring will be given a device on visit 2. Glucose level will be measured 3 times a day in the first week and thereafter once a week or as needed. Additional measurements are warranted in the case of hypo- or hyperglycemia signs or symptoms.

³ Safety blood samples include: Fasting blood samples (8hr fasting), Liver and kidney functions, urine dipstick for signs of infection and ketoacidosis (if positive leukocyte esterase (WBC) or nitrites a midstream urine sample for urine culture will be taken.

⁴ Echocardiography will be done if needed to verify patient suitability for inclusion criteria.

Trial Period	Screening	Treatment Period			
Visit	1	2	3	4	5
Study Week	0	8	16	20	28
Days from randomization	-56	0	56	84	140
Endocrinologist consult		X			
Biobank samples		X	X	X	X
Urine Analysis (Electrolytes)		X	X	X	X
24hr Urine Sample collection		X	X	X	X
CardioPulmonary Exercise Test & 6 minute walk distance ⁵		X	X		X
Adverse events		X	X	X	X

Study scheme

Visit 3
Analysis 1

Visit 5
Analysis 2

4.2.2 Visit Procedures

Screening visit (day -56 to 0)

1. Obtain patient signed informed consent.

Prior to a subject's participation in the trial, an Informed Consent form will be signed and personally dated by the subject and by the person who conducted the Informed Consent discussion.

If a subject is unable to read, an impartial witness should be present during the entire Informed Consent discussion. After the written Informed Consent form is read and explained to the subject and after the subject has orally consented to participating in the trial if the subject is capable of doing so she/he should sign and personally date the Informed Consent form, the witness should sign and personally date the consent form. By signing the consent form if the subject is unable to sign, then the witness attests that the information in the consent form was accurately explained to, and apparently understood by the subject and that Informed Consent was freely given by the subject.

Prior to participation in the trial, the subject will receive a copy of the signed and dated written Informed Consent form. During participation in the trial, the subject will receive a copy of the signed and dated consent form updates and a copy of any amendments to the written information provided to subjects.

The investigator should document in the source data that the Informed Consent was signed prior to subject's participation in the study and according to the ICH guidelines, as described above.

2. Review patient's eligibility for the study according to in- and exclusion criteria.
3. Demographic data will be recorded (sex, age, ethnic origin)
4. Review and record relevant medical history. Participant's medical history should be fully documented at screening, to ensure compliance with study inclusion criteria and the absence of circumstances mentioned in the exclusion criteria. Medical history information must include, but not be limited to, past and present major illnesses, any previous surgery/operations and any current ongoing illness.
5. Review and record current medical condition history (T2DM control, NYHA status, Heart failure therapy).
6. Perform a complete physical examination. The treating investigator will conduct a complete physical examination and assess subject's performance

status at screening in order to ensure compliance with study inclusion criteria and the absence of circumstance mentioned in the exclusion criteria.

7. Measure vital signs at screening in order to ensure compliance with study criteria. Vital signs measurements will include systolic and diastolic blood pressure, pulse rate, respiratory rate, and body temperature. Body weight and height will also be measured. Measurements that may potentially constitute future adverse events (e.g. hypoglycemia, hypotension etc.) should be graded in the medical history form at baseline according to CTC as described in [8.1.3 below](#).
8. Collect safety blood and urine samples. Including hematology and chemistry blood examinations and urine dipstick for signs of ketoacidosis or infection.
Hematology: Testing of Complete Blood Counts (CBC) including differential and platelet count will be performed at screening, in order to ensure compliance with study inclusion criteria (5 ml blood per sample). Every out-of-range value will be assessed by a physician and deemed as either clinically significant (S) or not significant (NS).
Chemistry: Serum chemistry panel will consist of sodium, potassium, calcium, protein, albumin, alanine aminotransferase (ALT), aspartate aminotransferase (AST), bilirubin, alkaline phosphatase, blood urea nitrogen (BUN), creatinine, and fasting glucose. Chemistry will be performed at screening, in order to ensure compliance with study inclusion criteria (5-10 ml blood per sample). Every out-of-range value will be assessed by a physician and deemed as either clinically significant (S) or not significant (NS).
11. Review menopausal status and in women of childbearing potential a urine pregnancy test (β -HCG) will be performed.
12. Collect venous blood will be drawn for HbA_{1c}.
13. Perform device interrogation by an electrophysiological technician for verification of arrhythmogenic risk according the eligibility criteria.
14. Perform monitor counter reset by an electrophysiological technician.
15. Perform echocardiography for verification of EF \leq 40% according to the eligibility criteria (if not done in the last 6 months).
16. Review concomitant medications. All prior treatments (medications) received by the subject within 30 days of the initial screening visit and during the study will be recorded on the subject's CRF including the name of the treatment, indication, total daily dose, frequency and the start and stop dates. Any medications (including prescription, over-the-counter, herbal supplements and health store products) to be taken during the study will be documented.

Collection of information on standard of care treatment will be done as part of medications records during the study.

17. Invite study subject to study site for Holter ECG installation in one of the 7 days before the next visit.

Base line visit (2) (day 0 ±7 days)

1. Patient's enrollment. Eligibility for the study according to inclusion and exclusion criteria will be rechecked but lab tests not repeated) if all criteria are fulfilled and there is no significant change in the subject's health, he/she will be enrolled into the study to receive the first study drug.
2. Get patient randomization number.
3. Begin study drug treatment (active or placebo), provide patient 60 tablets and give treatment instructions for home use.
4. Perform a complete physical examination.
5. Measure vital signs in order to ensure compliance with study criteria. Vital signs measurements will include systolic and diastolic blood pressure, pulse rate, respiratory rate, and body temperature. Body weight will also be measured. Measurements that may potentially constitute future adverse events (e.g. hypertension, fever etc.) should be graded in the medical history form at baseline according to CTC as described in [8.1.3 below](#)
6. Collect safety blood and urine samples. Including hematology and chemistry blood examinations and urine dipstick for signs of ketoacidosis or infection.
7. Review menopausal status and in women of childbearing potential perform a urine pregnancy test (β -HCG).
8. Collect home diary glucose results and provide a new diary for the following period.
9. Provide home diary for daily blood glucose determination.
10. Perform device interrogation.
11. Perform Monitor counter reset.
12. Collect Holter ECG device results and invite study subject to study site for Holter ECG installation in one of the 7 days days before the next visit.
13. Perform echocardiography for determination of EF
14. Consult endocrinologist for glucose lowering medication titration
15. Collect blood examination for NT-Pro-BNP
16. Collect urine and blood examination for biobank sample
17. Collect urine for electrolyte concentration

18. Obtain 24 hours urine sample collection
19. Perform cardiopulmonary exercise test (In case of inability to perform cardiopulmonary exercise test according to clinical judgment, patient will have a 6 minute walk distance test)
20. Perform 6 minute walk distance
21. Review concomitant medications.
22. Document adverse events.

Treatment washout visit (3) (day 56 ±7 days)

1. Provide patient with 30 tablets of study drug for home use
2. Collect study drug blisters returned by patient.
3. Measure vital signs in order to ensure compliance with study criteria. Vital signs measurements will include systolic and diastolic blood pressure, pulse rate, respiratory rate, and body temperature. Body weight will also be measured.
4. Collect safety blood and urine samples. Including hematology and chemistry blood examinations and urine dipstick for signs of ketoacidosis or infection.
5. Remind patient to follow the endocrinologist instructions given on visit 2.
6. Collect venous blood that will be drawn for HbA1c.
7. Collect home diary glucose results and provide a new diary for the following period.
8. Perform device interrogation.
9. Perform Monitor counter reset.
10. Collect Holter ECG device results and invite study subject to study site for Holter ECG installation in one of the 7 days days before the next visit.
11. Perform echocardiography for determination of EF
12. Collect blood examination for NT-Pro-BNP
13. Collect urine and blood examination for biobank sample
14. Collect urine for electrolyte concentration
15. Obtain 24 hours urine sample collection
16. Perform cardiopulmonary exercise test (In case of inability to perform cardiopulmonary exercise test according to clinical judgment , patient will have a 6 minute walk distance test)

17. Perform 6 minute walk distance
18. Review concomitant medications.
19. Document adverse events.

Treatment visit (4) (day 84 ±7 days)

1. Provide patient with 60 tablets of study drug for home use
2. Collect study drug blisters returned by patient.
3. Measure vital signs in order to ensure compliance with study criteria. Vital signs measurements will include systolic and diastolic blood pressure, pulse rate, respiratory rate, and body temperature. Body weight will also be measured.
4. Review menopausal status and in women of childbearing potential perform a urine pregnancy test (β -HCG).
5. Remind patient to follow the endocrinologist instructions given on visit 2.
6. Collect home diary glucose results and provide a new diary for the following period.
7. Perform device interrogation.
8. Perform Monitor counter reset.
9. Collect blood examination for NT-Pro-BNP
10. Collect urine and blood examination for biobank sample
11. Collect urine for electrolyte concentration
12. Obtain 24 hours urine sample collection
13. Review concomitant medications
14. Document adverse events.

End of Study visit (5) (day 140 ±7 days)

- 1.
2. Collect study drug blisters returned by patient.
3. Measure vital signs in order to ensure compliance with study criteria. Vital signs measurements will include systolic and diastolic blood pressure, pulse rate, respiratory rate, and body temperature. Body weight will also be measured.
4. Collect safety blood and urine samples. Including hematology and chemistry blood examinations and urine dipstick for signs of ketoacidosis or infection.
5. Review menopausal status and in women of childbearing potential perform a urine pregnancy test (β -HCG).
6. Collect venous blood that will be drawn for HbA1c.

7. Collect home diary glucose results.
8. Perform device interrogation.
9. Perform Monitor counter reset.
10. Collect Holter ECG device results.
11. Perform echocardiography for determination of EF
12. Collect blood examination for NT-Pro-BNP
13. Collect urine and blood examination for biobank sample
14. Collect urine for electrolyte concentration
15. Obtain 24 hours urine sample collection
16. Perform cardiopulmonary exercise test (In case of inability to perform cardiopulmonary exercise test according to clinical judgment , patient will have a 6 minute walk distance test)
17. Perform 6 minute walk distance.
18. Review concomitant medications.
19. Document adverse events.

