Evaluations consists of vital signs, laboratory assessments blood examination, device (ICD or CRTD/P) interrogation, 24h' Holter ECG in case of ICD/CRTD/P malfunction as a backup arrhythmia assessment and echocardiography. Patient's glucose level will be monitored by a home device 3 times a day in the first week and thereafter once a week or as needed. At visit 2, an endocrinologist consultant will give to the patient instructions for antidiabetic treatment titration according to [appendix 1](#).

Patients will be treated for up to 8 weeks with the study drug or placebo 10 mg/day every morning.

Washout period

Study subjects will stop study drug (empagliflozin/placebo) of the first treatment period and will be given placebo for a washout period of 4 weeks and will crossover to the second drug at the end of this period at the beginning of the next treatment period. During this period, patient's glucose level will be monitored by a home device 3 times a day in the first week and thereafter once a week or as needed. Safety laboratory examinations, HbA_{1c}, device interrogation and resetting, Holter ECG and echocardiography will be performed at the end of this period (visit 3). In the case of abnormal glucose levels during the washout period, diabetes treatment will be changed according to appendix 1 aiming to maintain glucose levels at normal range.

Second treatment period

Patients will crossover to empagliflozin or placebo treatment for a period of 8 weeks.

Evaluations consists of vital signs, laboratory assessments including pregnancy test for FCBP. Patient's glucose level will be monitored by a home device 3 times a day in the first week and thereafter once a week or as needed. Device (ICD or CRTD/P) interrogation and 24h' Holter ECG in case of ICD/CRTD/P malfunction as a backup arrhythmia assessment and echocardiography. In the case of abnormal glucose levels during the second treatment period, diabetes treatment will be changed according to appendix 1 aiming to maintain glucose levels at normal range.

Patients will be treated for up to 8 weeks with the study drug or placebo 10 mg/day every morning.

Medication compliance will be performed during the two treatment periods by counting the returned study drug blisters.

Accompanying scientific program

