7.1 PVCs Burden

The primary efficacy parameter to be assessed will be PVCs burden.

PVCs burden is defined as the PVCs percentage of all beats in a pre-specified period captured on ICD or CRTD/P device.

PVCs burden will be evaluated as a part of the device interrogation on visit 1 to assess device integrity and proper function, in visit 2 to assess patient's eligibility for the study according to in- and exclusion criteria. In visits 3 and 5 to assess for treatment efficacy.

Assessment of the PVCs will be based on PVC counters for the various ICD/CRTD/P interrogated (from Medtronic, St. Jude, Guidant – Boston Scientific, Biotronik). Monitor counter reset will be conducted on visit 1,2,3,4 and 5. The equation for calculating the PVC burden for monitoring providing the PVC number per period will be:

$$PVC\ Burden(\%) = \frac{Number\ of\ PVCs}{Average\ HR\ \left(\frac{beats}{minute}\right) * 60 * 24 * (\#days\ in\ the\ period\ assessed)}$$

For monitors providing the PVC burden per hour the calculation will be:

$$PVC\ Burden(\%) = \frac{Average\ \frac{PVC}{hour}}{Average\ Heart\ Rate\left(\frac{Beats}{Minute}\right) * 60}$$

In case of device malfunction, counter malfunction or any other cause of inability to readout the device PVC counter measurement, PVC burden will be

calculated from a 12 Lead ECG Holter for 24 hours conducted at one of the last 7 days of the period assessed and will be calculated as:

$$PVC\ Burden(\%) = \frac{Number\ of\ PVCs}{Average\ Heart\ Rate\ \left(\frac{beats}{minute}\right) * 60 * 24}$$

Monitor counter readout and resetting will be performed by an electrophysiologist technician; data will be entered into the CRF by the study coordinator after approval of the principal investigator.

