7.2 Non-sustained ventricular tachycardia (NSVT)

Non-sustained ventricular tachycardia number is defined as the NSVT number in a pre-specified period captured on ICD or CRTD/P device interrogation, or as a backup information (in case of ICD or CRTD/P malfunction) on Holter ECG. The device will be activated during the whole study period and data will be captured on the CRF at visits 1 to 5. The Holter ECG device of 24 h' will be performed in case of device malfunction, counter malfunction or any other cause of inability to readout the device PVC counter measurement. Holter assessment will be conducted at one of the last 7 days of the period assessed. Data from study device/Holter will be captured on the CRF at visits 2, 3 and 5.

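### The visit lists arrange a Holter before visit 4 and none before visit 5, so the backup for the primary endpoint in period 2 may not exist when it is needed

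*Combined protocol and SAP*

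**What the plan says.** The primary endpoint is PVC burden from the device counter. Section 7.1 provides one substitute when the counter cannot be read: burden is "calculated from a 12 Lead ECG Holter for 24 hours conducted at one of the last 7 days of the period assessed". Sections 7.2 and 7.3 apply the same timing to NSVT and to sustained VT, and section 7.2 adds: "Data from study device/Holter will be captured on the CRF at visits 2, 3 and 5".

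Table 2 (section 4.2.1) has a row for "12 Lead Holter ECG for 24hrs", marked at visits 2, 3 and 5 by column position, with no condition attached.

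The visit lists in section 4.2.2 handle Holter as follows:

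- Visit 1, item 17: invite the patient for installation in the week before visit 2.
- Visit 2, item 12: collect the results, then "invite study subject to study site for Holter ECG installation in one of the 7 days days before the next visit". Here the next visit is visit 3.
- Visit 3, item 10: the same instruction. Here the next visit is visit 4.
- Visit 4: 14 items, none of which mentions Holter.
- Visit 5, item 10: "Collect Holter ECG device results".

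For both treatment periods, section 4.2 describes "24h' Holter ECG in case of ICD/CRTD/P malfunction as a backup arrhythmia assessment". The washout paragraphs in the synopsis and section 4.2 also mention a Holter at the end of washout but label that time point visit 3, which is where washout begins.

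**The concern.** The instruction at visit 3 points to the wrong week. It arranges a recording on washout treatment, before the first period 2 dose, and nothing in the lists arranges the recording that visit 5 is supposed to collect. Coordinators usually work from the visit lists, so the backup for period 2 could be absent even though the rest of the protocol assumes it.

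The conditional wording adds to the problem. If Holter is done only after a malfunction, and the malfunction is discovered at the visit that closes the period, the 7-day window has already passed.

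At stake is the period 2 value of the primary endpoint for each patient with an unreadable counter. The planned primary test is paired, so a patient without a period 2 value contributes nothing to it. Section 9.2 would still count that patient in the ITT population, which needs only one post-baseline assessment. Section 4.4.1 does not replace withdrawn patients, and a recording not made during a period cannot be recovered afterwards.

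**Working it through.** **1. Nominal windows.** Visits 2, 3, 4 and 5 are at days 0, 56, 84 and 140 (Table 2). Each Holter window is the visit day minus 7 up to the visit day.

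| Visit | Closes | Window (days) | Arranged in 4.2.2? | In Table 2? |
|---|---|---|---|---|
| 2 | screening | -7 to 0 | yes, at visit 1 | yes |
| 3 | period 1 | 49 to 56 | yes, at visit 2 | yes |
| 4 | washout | 77 to 84 | yes, at visit 3 | no |
| 5 | period 2 | 133 to 140 | no | yes |

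The lists and the table agree for the first two rows and are exactly reversed for the last two. The arranged recording is 140 - 84 = 56 days too early.

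**2. Do the visit windows rescue it?** The headings allow "Treatment visit (4) (day 84 ±7 days") and "End of Study visit (5) (day 140 ±7 days"). The latest visit 4 is day 84 + 7 = 91. The earliest visit 5 is day 140 - 7 = 133, whose Holter week begins at day 126. The gap is still 126 - 91 = 35 days. Period 2 tablets are dispensed at visit 4, so any recording before that visit precedes period 2 dosing.

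**3. Can a malfunction-triggered Holter work?** Table 2 schedules interrogation only at visits, with none between visits 2 and 3 or between visits 4 and 5. A failure first seen at visit 3 or visit 5 is seen when the window is closing. In period 1 this does no harm if the lists are followed, because visit 2 invites every patient. In period 2 no such invitation exists.

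**4. The plan's own power figure.** Section 9.1 uses a difference of 10, a standard deviation of differences of 40, N = 128 and two-sided alpha of 0.05. The normal approximation gives N = (40 × (1.960 + 0.842) / 10)², which rounds up to 126. The noncentral t with N - 2 = 126 degrees of freedom and noncentrality 10 / (40/√128) = 2.828 gives power 80.1%. The stated figure reproduces.

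**5. Illustration if period 2 values are missing.** Let f be the fraction of patients with an unreadable counter in period 2 and no valid Holter. The documents give no value for f. Assume these patients drop out of the paired test, failure is unrelated to treatment, and the difference and standard deviation are unchanged. The noncentrality is then 10√n / 40, with n - 2 degrees of freedom.

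| f (assumed) | Lost | n | Power |
|---|---|---|---|
| 0 | 0 | 128 | 80.1% |
| 5% | 6 | 122 | 78.2% |
| 10% | 13 | 115 | 75.7% |
| 20% | 26 | 102 | 70.6% |

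The upper rows are the more plausible, for the reasons given under the objection.

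**The case against.** The strongest reply is that the intent is clear from the rest of the document. Table 2, the timing rule in section 7.1, the capture visits in sections 7.2 and 7.3, and the collection item at visit 5 all point to a recording before visit 5. A site working from Table 2 would obtain it. That is true, but it shows only that the visit lists contradict the other sections. It does not correct the lists.

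The second reply concerns reach. Eligible devices must be able to record PVC burden, evidence of ICD malfunction is an exclusion, devices are interrogated at visits 1 and 2, and section 4.5 lists device malfunction as a possible reason to end participation. This stands and probably keeps the number small. It does not bring the number to zero, because the trigger in section 7.1 covers any inability to read the counter, which is wider than malfunction.

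Three stronger readings are tempting and are not supported:

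- A reader might infer that washout recordings will be analysed as period 2 values. Section 7.1 rules that out, since the recording must come from the last 7 days of the period assessed. If it did happen to every affected patient, with no carry-over and washout burden equal to placebo, only the placebo-first half would lose the effect. The expected difference would be 10 × (1 - f/2), and power would be 78.1% at f = 5% and 76.0% at f = 10%.
- A reader might infer that the backup fails in both periods unless Table 2 is followed. It does not fail in period 1, where the lists invite every patient.
- A reader might infer that pairing a 24-hour Holter with an 8-week device average biases the treatment effect. With 1:1 allocation to sequence, and failure unrelated to treatment, Holter would replace the device about equally often under each treatment. A systematic difference between sources would then largely cancel in the mean and leave mainly added noise.

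**Conclusion.** The contradiction is established by the text. Section 4.2.2 arranges a Holter for the last week of washout and none for the last week of period 2, against Table 2 and section 7.1. The consequence is conditional: if a site follows the visit lists literally, a patient whose counter cannot be read in period 2 has no valid backup value for the primary endpoint. NSVT and sustained VT, which rely on the same Holter, are affected in the same way.

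The size depends on a failure rate that the documents do not give. It is likely to be small, and the power figures above are illustrations under stated assumptions. The sample size calculation itself is not in question. The malfunction-only wording is a related defect: it cannot deliver a recording when the failure is first found at the closing visit. The point merits correction because the loss concerns the primary endpoint, cannot be reversed, and is almost free to prevent.

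**What to change.** 1. Add to the visit 4 list an invitation for Holter installation in the 7 days before visit 5.
2. Remove the invitation from the visit 3 list, unless an end-of-washout Holter is intended. If it is, add it to Table 2, add a collection item at visit 4, and state that it does not serve as a period 2 value.
3. State in the synopsis and in sections 4.2, 7.2 and 7.3, as Table 2 already implies, that Holter is recorded routinely before visits 2, 3 and 5, and is used for the endpoints only when the device reading is unavailable.
4. Reconcile the washout paragraphs in the synopsis and section 4.2, which place the assessments at the end of washout but label them visit 3.
5. Optionally, add a sensitivity analysis that uses same-source pairs or excludes mixed device-Holter pairs. Replacing a valid 8-week device value with a 24-hour Holter value in the primary analysis is a debatable trade, because the Holter pair is noisier, and it is not needed to resolve this point.

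The cost is a few lines of text in the visit lists and design paragraphs, plus one sentence if the sensitivity analysis is adopted. No recordings are added beyond those in Table 2, unless the sponsor wants the end-of-washout Holter.

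### The visit lists book the last Holter before visit 4 instead of visit 5, against Table 2 and section 7.1, so no visit step arranges the period 2 backup for the primary endpoint

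*Combined protocol and SAP*

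**What the plan says.** Table 2 (section 4.2.1) has a row for "12 Lead Holter ECG for 24hrs" with marks at visits 2, 3 and 5 and none at visit 4. Section 7.1 makes the Holter the substitute for the primary endpoint whenever the device's PVC counter cannot be read. The burden is then "calculated from a 12 Lead ECG Holter for 24 hours conducted at one of the last 7 days of the period assessed". On the efficacy read-outs, section 7.1 says: "In visits 3 and 5 to assess for treatment efficacy". Section 7.2 states, and 7.3 repeats: "Data from study device/Holter will be captured on the CRF at visits 2, 3 and 5". Section 4.2 includes in the second treatment period a "24h' Holter ECG in case of ICD/CRTD/P malfunction as a backup arrhythmia assessment and echocardiography".

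The step-by-step lists in section 4.2.2 work by invitation. Visit 1 item 17 invites the patient for a Holter before visit 2, and visit 2 item 12 does so for visit 3. Visit 3 item 10 collects the period 1 recording and again says to "invite study subject to study site for Holter ECG installation in one of the 7 days days before the next visit". The visit 4 list, whose heading begins "Treatment visit (4) (day 84 ±7 days", has 14 items, and none mentions a Holter. Visit 5 item 10 reads "Collect Holter ECG device results".

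**The concern.** From visit 3 the next visit is visit 4, at the end of washout. Followed literally, the lists send the patient for a Holter in the last week of washout. Table 2 does not ask for that recording and no step collects it. The lists then book nothing for the last week of treatment period 2, which is where section 7.1 needs the backup.

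Timing makes this matter. The Holter has to be worn before the visit at which the counter is read. If the counter first proves unreadable at visit 5, the last 7 days of the period have already passed and the recording cannot be made afterwards. The main analysis in section 9.2.1 is a paired t-test or signed-rank test, so a patient without a period 2 value drops out of it. Section 4.4.1 does not replace withdrawn subjects, and section 9.1 states no allowance for dropout.

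**Working it through.** **Visit lists against the schedule**

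| Visit (day) | Holter in Table 2 | List collects a Holter | List invites for a Holter before |
|---|---|---|---|
| 1 (−56) | no | no | visit 2 (item 17) |
| 2 (0) | yes | yes (item 12) | visit 3 (item 12) |
| 3 (56) | yes | yes (item 10) | visit 4 (item 10) |
| 4 (84) | no | no | none |
| 5 (140) | yes | yes (item 10) | not applicable |

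Collection agrees with Table 2 at every visit. The invitations agree for visits 2 and 3 and then fail twice: one points to visit 4, where none is scheduled, and none points to visit 5, where one is.

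**Which patients are exposed**

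A period 2 value is lost only if all of these hold:

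1. The counter is unreadable at visit 5.
2. The failure was not visible at visit 4, where the device is also interrogated and reset (visit 4 items 7 and 8). A failure seen there leaves 8 weeks to arrange the Holter.
3. The patient was not taken off study under section 4.5, which lists device malfunction as a reason for stopping. A counter that cannot be read in a device that otherwise works is not clearly covered by that rule.
4. The site followed the visit lists and not Table 2, so that no Holter was worn.

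**The plan's own sample size**

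Inputs from section 9.1: difference 10, SD of differences 40, two-sided alpha 0.05, power 80%, 64 per sequence, N = 128.

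- Normal approximation: N = ((1.960 + 0.842) × 40/10)² = 125.6, so 126.
- t-based: SE = 40/√128 = 3.536, noncentrality = 10/3.536 = 2.828, df = 126, power = 80.1%.

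The stated 128 at 80% power reproduces.

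**Power if pairs are lost**

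The documents give no rate of unreadable counters, so the shares below are assumptions. Each is the share of all 128 patients who meet all four conditions. Noncentrality = 10/(40/√N), df = N − 2.

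| Assumed share lost | Complete pairs N | Noncentrality | Power |
|---|---|---|---|
| 0% | 128 | 2.828 | 80.1% |
| 2% | 128 × 0.98 = 125.4, so 125 | 2.795 | 79.2% |
| 5% | 128 × 0.95 = 121.6, so 122 | 2.761 | 78.2% |
| 10% | 128 × 0.90 = 115.2, so 115 | 2.681 | 75.7% |

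The 10% row is an outer bound for illustration. Conditions 2 to 4 each reduce the share below the raw rate of unreadable counters.

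**The case against.** A reader might infer that the period 2 Holter is not performed at all, and that any unreadable counter leaves period 2 without a value. The documents do not support that. Table 2, visit 5 item 10, and sections 4.2 and 7.1 to 7.3 all provide for a Holter in period 2. Section 4.2 also says that assessments follow the table of procedures. A site working from Table 2 would probably do the recording. Entry requires a device that can record PVC burden and excludes ICD malfunction, and the visit 4 interrogation catches earlier failures. All of this stands and limits the point to an operational risk in a small group.

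A reader might also infer bias, because only period 2 is exposed. Under 1:1 allocation the lost values are empagliflozin for one sequence and placebo for the other. Nothing in the documents shows that this favours either treatment.

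Finally, the visit 3 invitation may be deliberate. The washout text in the synopsis and in section 4.2 puts a Holter at the end of washout, though it labels that visit 3, and in Table 2 washout ends at visit 4. The other assessments named there (safety laboratory tests, HbA1c, echocardiography) sit at visit 3 and not visit 4 in Table 2, which suggests that the visit label is right and the timing phrase is wrong. The text does not settle it. Even if an end-of-washout Holter is wanted, visit 4 would still need to collect it and to invite for visit 5.

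**Conclusion.** The contradiction is certain: the visit lists in section 4.2.2 disagree with Table 2 and section 7.1 on where the last Holter belongs, and no visit step arranges the one before visit 5. The consequence is conditional. A patient may lose the period 2 value, and with it a place in the paired primary comparison, only if the counter first proves unreadable at visit 5, section 4.5 has not already removed the patient, and the site relied on the lists. Under assumed losses of 2% and 5% of pairs, power falls by about 1 and 2 percentage points from 80.1%. These figures use section 9.1's own effect and SD, and the loss rates are assumptions. The point is worth acting on because the Holter is the only stated backup for the primary endpoint and also backs up the NSVT and sustained VT counts. It is an inconsistency to correct and not a flaw in the design.

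**What to change.** - Add an item to the visit 4 list that invites the patient to the site for Holter fitting on one of the 7 days before visit 5.
- Reconcile the visit 3 invitation with Table 2 and with the washout text in the synopsis and section 4.2. Either delete the invitation and correct the timing phrase, or, if an end-of-washout Holter is intended, add its collection to visit 4 and a mark to Table 2.
- State whether the Holter is routine, as in Table 2 and the visit lists, or done only on malfunction, as in sections 4.2, 7.2 and 7.3. A Holter triggered only by a failure found at visit 5 comes too late for the window in section 7.1.
- Reconcile device malfunction as a trigger for the Holter backup (section 7.1) with device malfunction as a reason for discontinuation (section 4.5).

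The cost is a few lines of text. If the visit 3 invitation is deleted, patients wear the number of Holters that Table 2 already plans. If an end-of-washout Holter is kept, the cost is one further recording per patient beyond Table 2.
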